Biologic samples (blood draws, cheek swabs, saliva samples, tissue samples, etc.) – Tubes containing blood samples and cerebrospinal fluid (CSF) tubes will be labeled with the subject's ID code, date of draw, and time of draw. Samples will be transported by engaged study staff to the appropriate processing lab at WUSM before being shipped to [name] lab in batch.

H Study Monitoring, Auditing, and Inspecting

Oversight of the study will be the responsibility of the PI and his delegates, including the study coordinator(s). Internal self-audits for quality assurance purposes may be conducted as necessary to ensure study procedures are being followed and for the integrity of the data. The study will also be reviewed at least annually by HRPO/WU IRB.

I Study Administration

I.1 Funding Source and Conflicts of Interest

Funding is through an R01 through the National Institute of Mental Health (NIMH) at NIH.

I.2 Subject Stipends or Payments

Participants may be remunerated for completing all assessments as follows:

- MRI = \$75
- Neuropsychological assessments = \$60
- Questionnaires = \$15
- Laboratory evaluations = \$25
- Stool sample and dietary survey = \$25
- Lumbar Puncture = \$75

Participants may be remunerated after completing each procedure rather than having to wait until the end of the study to receive their full remuneration. If a participant completes all study procedures, they will be paid a total of \$275.

Remuneration for the neuropsychological assessments may be prorated, based on the per cent of assessments that are completed; for example, if an individual only completes half (50%) of the assessments, they may only receive half of the payment (\$30.00). If a participant does not complete the MRI, laboratory evaluations or lumbar puncture, they may not be paid, however, if they make a good-faith effort and are unable to complete, they may be remunerated.

In our experience, the biggest barrier to study retention has been access to transportation, not untimely or inadequate reimbursement. Consequently, we have included the costs of taxis into our budget and intend to provide these services to all participants upon request. These exact methods and amount of participant remuneration have been employed in multiple studies conducted in our lab over the past ten years.

I.3 Study Timetable

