A total of 160 PLWH (80 regular cannabis users and 80 non-users) and 160 demographically similar healthy HIV- controls (80 regular cannabis users and 80 non-users) may undergo multimodal neuroimaging, immunophenotyping (including blood and cerebrospinal fluid), and neuropsychological testing to address the specific aims. PLWH may be recruited from WUSTL Infectious Disease (ID) Clinic, the AIDS Clinical Trial Unit (ACTU), Volunteers for Health, The Spot, other area providers and by hanging flyers at various places in the community. HIV- controls may be recruited from similar demographic communities as the PLWH, as well as Volunteers for Health and the surrounding community and social organizations.

D2 Subject Selection and Withdrawal

D2.1 Inclusion Criteria

(1) Participants must be 18–70 years old.

- (2) PLWH must have documented HIV infection for approximately 1 year, be on a cART regimen for approximately ≥ 3 months, and be virally well-controlled (< 200 copies/mL).
- (3) HIV- controls must have confirmed HIV- serostatus.
- (4) Participants must complete at least 9 years of education.
- (5) Participants must be able to provide informed consent.
- (6) Female participants must have a negative pregnancy test or written documentation of tubal ligation, hysterectomy, post-menopausal status, etc. and cannot be breastfeeding.
- (7) Participants should have no contraindications to an MRI scan.
- (8) Participants should be willing to have cannabis use history confirmed via clinical interview and urine analysis.
- (9) All inclusion criteria at PI discretion.

D2.2 Exclusion Criteria

- (1) History of neurological disorder (e.g., stroke, epilepsy, head injury with loss of consciousness for > 5 minutes, developmental learning disability, etc.).
- (2) Uncontrolled major affective disorder; any history of schizophrenia. Major depression or Bipolar disorder controlled with no hospitalizations and suicidal ideation in the past year is allowed.
- (3) Current substance use disorder (SUD) other than cannabis use disorder (CUD) and mild Alcohol Use Disorder as defined by DSM-5 criteria. A past SUD approximately > 1 year before the time of study enrolment may be allowed.
- (4) currently prescribed anti-coagulants (only exclusionary if participant will engage in optional LP).
- (5) an allergy to lidocaine or similar anesthetic (only exclusionary if participant will engage in optional LP).

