Once a person is deemed eligible, individuals will be given a more detailed description of the study including possible risks and benefits, either over the phone or in person. As part of the screening process, a medical record review may also be completed to fill in and confirm documented HIV+ status and length of time on cART and viral suppression (for PLWH); and presence of any medical condition or other criterion that would meet exclusion criteria or make it unsafe to participate in the study.

HIV negative healthy controls that are demographically matched as much as possible will be recruited from the friends, family and partners of their HIV+ counterparts, as well as from various community organizations as described above.

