Based on our previous experience, we believe approximately 1,200 participants may need to be initially screened by phone to reach a sample size of 320 individuals. Before signing consent or undergoing study procedures a clinician or study staff will evaluate participants for acute intoxication. If acute intoxication is suspected the participant may be rescheduled. At the on-site visit the following will be obtained: (1) informed consent; (2) urine sample for drug screen, urine cannabinoids and metabolites, and pregnancy test (for all pre-menopausal female participants without documentation of tubal ligation, hysterectomy, or menopause); (3) oral HIV test (for HIV- controls only); (4) medical record review; (5) assessment of mental health and performance of activities of daily living; (6) multi-dimensional assessment of substance use; and (7) MRI metal screening form. The urine sample will be tested using the Rapid Drug Screen (RDS). The RDS detects cannabis, amphetamines, cocaine, opiates, barbiturates, methamphetamines, benzodiazepines, and phencyclidine. Any discrepancies amongst any dimensions of substance use may be brought to case conference for consensus diagnosis. If the participant is not severely depressed (BDI-II < 29), has a negative urine screen other than THC, and has no MRI contraindications; then s/he may be enrolled. Based on our previous experience we believe approximately 30 individuals may be ineligible due to depression scores or non-cannabis substance use, leading to the final sample size of 320 participants. After consent and completion of assessments above, each enrolled study participant may receive the following procedures during this on-site visit (~6 hours): a neuromedical examination, serum laboratory tests, neuropsychological performance testing, questionnaires, and neuroimaging. A follow-up lumbar puncture (LP) may be scheduled ~ 1 week or more after the primary visit.

We have found that it is especially important to try to accommodate our participants' requests regarding their study visit. The assessment schedule designed for this proposal has the necessary flexibility to adapt to the real-life complexities of working with clinical populations. Through flexible scheduling, barrier mitigation, and positive feedback, this study minimizes the extent to which a participant's daily life issues adversely impact their ability to complete scheduled visits. Reducing

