Aim 1: *Hypothesis 1a.* The effect of regular cannabis use on peripheral and brain inflammatory markers (primary response: composite markers; secondary: individual inflammatory markers) will be analyzed using linear models (analysis of covariance), including as predictors cannabis status, HIV, and their interaction. If an interaction effect between cannabis and HIV status is not significant, additive effects will be evaluated. Demographic factors such as Wide Range Achievement Test (WRAT)-4, sex, and age will be examined as explanatory variables and incorporated into the final models if significant at $p < 0.20$ on backward model selection. Secondary marker analyses will control for multiple tests by keeping the overall FDR at level $\alpha = 0.05$. The effect of cannabis on peripheral and brain inflammatory markers among PLWH and HIV- controls will be reported based on these models using a 95%CI. In the absence of a HIV-by-cannabis interaction, the additive effects of cannabis and HIV are of primary interest. If an interaction is present, then the primary comparison will be between CB+ and CB- groups among PLWH (at $\alpha = 0.05$). Secondary analyses will compare the PLWH, CB+ to the other two groups (at familywise error rate $\alpha = 0.05$).

Hypothesis 1b. The relationship between cannabis exposure (KMSK and urine analysis of cannabis metabolites) and peripheral and brain immune activity markers (primary response: composite markers; secondary: individual markers, possibly log-transformed, as noted above) will be analyzed among regular cannabis users using linear models. Demographic factors such as the WRAT-4, sex, and age will be examined as explanatory variables and incorporated into the final models if significant at $p < 0.20$ on backward model selection. In addition to linear effects, non-linear cannabis effects will also be considered, including quadratic effects and smooth effects fitted via generalized additive models. Possible interactive effects between cannabis exposure levels and HIV will also be examined.

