Hypothesis 1b. We have $\geq 80\%$ power to detect an association between cannabis exposure and peripheral immune activity markers explaining $R^2 = 0.047$ or more of the variance in the response, corresponding to a small Pearson correlation coefficient of $r = 0.219$ or higher. This effect size is achievable. In our preliminary data, we observed higher correlation levels (Figure 4). For brain inflammatory activity

markers the corresponding values are $R^2=0.069$, $r=0.262$. The power calculations used statistical software (G*Power).

Hypothesis 1c: Sample size determination for classifier development aims will seek to improve predictor accuracy and significance.⁹⁸ Sample size determinations were conducted using proposed published methods. Training and testing errors of cross validated progressively sampled models will be assumed to follow power laws and will be evaluated based on asymptotic error value convergence to identify appropriate sample sizes.^{99, 100} Results will be optimized based on nonlinear weighted least squares fitting.¹⁰¹ Cross validated model performance will be compared using empirical and uniform priors to determine the effect of balanced classes.¹⁰² Cross validation of data with randomly permuted labels will be used to identify the significance of model results.¹⁰³

Aim 2:

Hypothesis 2a: The effect of cannabis and HIV on cognition will be quantified through linear models, similar to those discussed under Hypothesis 1a, adjusting for confounding factors. The main NP outcomes of interest are raw scores from the working memory/executive function domain scores. Secondary outcomes are cognitive domain-specific scores and global deficit score, with FDR control, as discussed above. We expect to find additive but not interactive effects of HIV and cannabis use on primary NP outcomes. Separate analyses will examine the effect of cannabis on NP outcomes, controlling for peripheral immune indices.

Analyses of brain volumetrics will focus on the hippocampus as the primary outcome. Secondary outcomes will include the caudate, amygdala, putamen, and pre-frontal regions (with FDR corrections). These volumetric analyses will follow a similar pattern to that described for NP outcomes.

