Hypothesis 2b: The effect of THC and CBD concentrations among cannabis users on NP and brain volumetrics will be analyzed using linear models. Demographic factors such as the WRAT-4, sex, and age will be examined as explanatory variables and will be incorporated into the final models if significant at $p<0.20$ in backward model selection. Possible non-linear cannabis effects will be explored, including quadratic effects and smooth effects fitted via generalized additive models. A possible interaction between cannabis exposure levels and HIV will also be examined.

Hypothesis 2c: Data-driven feature selection methods⁹²⁻⁹⁵ will be performed to reveal highly dimensional mechanisms and associations between cannabis use and brain integrity (cognition and volumetrics) that differentiate HIV serostatus from regular cannabis use. The analysis will yield a subset of biomarkers that are most indicative of the effects of cannabis on brain integrity (NP and volumetrics), while excluding irrelevant and redundant biomarkers. Continuous variables will be normalized to zero mean and unit variance. Features will be scaled independently to a common interval to ensure that features with higher magnitudes are not given preference during training. All analysis will be conducted with 10-fold cross validation with 10 repeats to ensure the reliability of the results.⁹⁶ Individual models will be trained with a categorical cross entropy loss function, and evaluated based on sensitivity, specificity, and receiver operator curve (ROC) area under the curve (AUC) F1 analyses. Models will be compared using the mean misclassification rate and Bayesian information criteria.⁹⁷ All analysis will be performed in common programming languages and packages (MATLAB, Python, and R).

Power Analysis for Aim 2:

Hypothesis 2a: With the proposed sample size of $n=320$ we have $\geq 80\%$ statistical power to detect additive effects of HIV status and cannabis use on NP and volumetrics outcomes corresponding to Cohen's $d=0.314$ each. This effect size is consistent with those determined in our preliminary data (Cohen's $d=0.584$ for cannabis and $d=0.418$ for HIV in *Figure 5*).

Hypothesis 2b: We have $\geq 80\%$ power to detect an effect of cannabis exposure among cannabis users on NP or volumetric outcomes corresponding to $R^2=0.047$ proportion of variance explained, or equivalently

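### Some HIV- controls are to come from the friends, family and partners of PLWH, but the Hypothesis 1a and 2a models and power figures assume that all participants are independent

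*Combined protocol and SAP*

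**What the plan says.** Two sections describe where HIV- controls come from, and they differ. D3.1 (Recruitment) says that demographically matched controls "will be recruited from the friends, family and partners of their HIV+ counterparts", and in the same sentence adds community organizations as a further source. D1 (Design Summary) says only that "HIV- controls may be recruited from similar demographic communities as the PLWH, as well as Volunteers for Health and the surrounding community and social organizations". Neither gives the share from each source, says whether the HIV+ counterpart must also be enrolled, or provides for recording who is linked to whom.

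In section F, Hypothesis 1a says that the inflammatory markers "will be analyzed using linear models (analysis of covariance), including as predictors cannabis status, HIV, and their interaction". Hypothesis 2a says that the effect of cannabis and HIV on cognition "will be quantified through linear models, similar to those discussed under Hypothesis 1a, adjusting for confounding factors", and the volumetric analyses follow the same pattern. Section F has no pair, household or family term, no random effect and no cluster-robust standard error. The power paragraphs give detectable effects of d = 0.634 (peripheral) and 0.758 (brain) for the HIV-by-cannabis interaction, and d = 0.314 each for "additive effects of HIV status and cannabis use on NP and volumetrics outcomes". They mention no correlation between participants.

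**The concern.** Partners and relatives can share a home, diet, infections, education and, for relatives, genes. If a person with HIV and a referred partner, relative or friend both enrol, their outcomes may stay correlated after adjustment for age, sex and WRAT-4. An ordinary linear model treats them as two unrelated people. Its standard errors can then be off, in a direction that depends on the contrast.

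The contrasts concerned carry weight. The interaction test decides how Aim 1 is read, the additive effects are of primary interest when no interaction is found, and Aim 2 expects additive effects. An interval that is too narrow for cannabis would overstate the evidence. One that is too wide for HIV or the interaction would give away precision the study has paid for.

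**Working it through.** **Inputs from the documents.** Four cells of 80 (D1), two-sided alpha of 0.05 (F), and 70% lumbar puncture completion (Power Analysis for Aim 1), which gives 0.70 × 80 = 56 per cell for brain markers.

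**Step 1: the plan's own figures.** With independent observations and a noncentral t, the noncentrality is d√(n/4) for the difference-in-differences (n per cell), d√(N/4) for an additive effect, and d√(n/2) for a two-cell comparison.

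- Interaction, peripheral: 0.634 × √20 = 2.835, power 80.7%.
- Interaction, brain: 0.758 × √14 = 2.836, power 80.6%.
- Additive effect: 0.314 × √80 = 2.809, power 80.0%.
- CB+ versus CB- among PLWH: d = 0.446 gives 80.1% and d = 0.533 gives 79.8%.

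The figures are correct on their own inputs, and those inputs include independence.

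**Step 2: effect of links.** Three quantities are not in the documents and are assumed: f, the share of the 160 controls linked 1:1 to an enrolled PLWH; rho, the within-pair residual correlation; and c, the share of pairs with the same cannabis status. Variances are taken as equal, with no links among PLWH.

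The HIV effect is a difference between two means of 160. Each of the 160f linked pairs subtracts 2rho/160² from its variance, so the variance is (2/160)(1 − f·rho). For the additive cannabis effect a concordant pair adds that amount and a discordant pair subtracts it; for the interaction the signs swap. The ratios of true to model variance are:

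- HIV: 1 − f·rho
- Additive cannabis: 1 + f·rho·(2c − 1)
- Interaction: 1 − f·rho·(2c − 1)
- CB+ versus CB- among PLWH: 1, because no control enters

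The false-positive rate of the ordinary test is 2[1 − Φ(1.96/r)], where r is the square root of the ratio. Each cell shows r, then that rate.

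| f, c, rho (assumed) | HIV | Additive cannabis | Interaction |
|---|---|---|---|
| 0.25, 1, 0.2 | 0.975, 4.4% | 1.025, 5.6% | 0.975, 4.4% |
| 0.5, 0.5, 0.3 | 0.922, 3.4% | 1.000, 5.0% | 1.000, 5.0% |
| 0.5, 0.75, 0.3 | 0.922, 3.4% | 1.037, 5.9% | 0.962, 4.2% |
| 0.5, 1, 0.3 | 0.922, 3.4% | 1.072, 6.8% | 0.922, 3.4% |
| 0.5, 0, 0.3 | 0.922, 3.4% | 0.922, 3.4% | 1.072, 6.8% |
| 1, 1, 0.3 | 0.837, 1.9% | 1.140, 8.5% | 0.837, 1.9% |
| 1, 1, 0.5 | 0.707, 0.6% | 1.225, 11.0% | 0.707, 0.6% |

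Simulation of the planned model (4,000 runs; f = 0.5, c = 1, rho = 0.3) gave 6.2% for cannabis, 3.3% for HIV, 3.5% for the interaction and 4.7% for the comparison within PLWH.

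**Step 3: power at f = 0.5, c = 1, rho = 0.3.** The critical value is 1.967.

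- Ordinary model, HIV: Φ((2.809 − 1.967)/0.922) = 82%.
- Ordinary model, interaction: Φ((2.835 − 1.967)/0.922) = 83%.
- Pair-aware model: the HIV and interaction variances become 1/[(1 − f) + f/(1 − rho)] = 1/(0.5 + 0.714) = 0.824 of the independent value, a standard-error ratio of 0.907. HIV power is Φ(2.809/0.907 − 1.967) = 87%, and interaction power is Φ(2.835/0.907 − 1.967) = 88%.
- Pair-aware model, additive cannabis: the factor is 1/[0.5 + 0.5/1.3] = 1.130, a ratio of 1.063, and power at d = 0.314 is Φ(2.809/1.063 − 1.967) = 75%.

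Keeping the ordinary estimate with cluster-robust standard errors recovers slightly less: Φ(2.809/0.922 − 1.967) = 86% for HIV. At f = 0.25, c = 1, rho = 0.2, every change in power or false-positive rate is under 3 percentage points.

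**The case against.** The best defence is that nothing shows links will be common. D3.1 also names community organizations, D1 names only community sources, and flyers and social media are planned. That the counterparts are themselves enrolled is an inference. Covariates would absorb some of what pairs share, so the residual correlation could be small. At 10% linked with rho = 0.1, no standard error changes by more than about 0.5%. In the fully concordant cases the ordinary model keeps at least the promised 80% power for HIV and the interaction, so the loss there is forgone precision rather than a shortfall.

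All of this stands, and it rules out several stronger readings. A reader might infer that the standard errors are wrong as a matter of fact. The documents support only that they can be, since f, rho and c are not given. A reader might infer that every primary comparison is affected. CB+ versus CB- among PLWH, which is primary when an interaction is present, is not. A reader might also take the additive cannabis test to be anti-conservative in general. That needs mostly concordant pairs, and the matching described is demographic, not on cannabis.

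The defence does not show that links will be rare, and the plan collects nothing that would let anyone show it afterwards.

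**Conclusion.** The point holds in conditional form. The recruitment plan allows linked participants; the Hypothesis 1a and 2a models and their power figures do not. The HIV effect is tested too conservatively whenever linked residuals are positively correlated, whatever the cannabis concordance. The additive cannabis effect and the interaction are biased in opposite directions, by an amount that is zero at 50% concordance and changes sign below it.

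The size ranges from negligible (a quarter linked, rho = 0.2) to moderate (half linked, full concordance, rho = 0.3: cannabis false-positive rate about 6.8%, HIV and interaction power about 82-83% instead of 87-88%). A false-positive rate near 11% needs almost every control linked with rho = 0.5. It should not be read as the expected case, because D3.1 itself names other sources. The power arithmetic is not in error; its independence assumption is unstated. The calculation assumes 1:1 links, so several controls linked to one PLWH, or links among PLWH, would change the figures.

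**What to change.** - Reconcile D1 and D3.1 on control sources, and state the share of linked controls expected.
- Record a coded linked-set number for each participant, covering referral, household and family links; unlinked people form their own set. The address on the locator form (E2) is not enough, because it misses friends and relatives who live apart.
- Fit the additive and interaction models of Hypotheses 1a and 2a with the same fixed effects plus a random intercept for linked set, or with cluster-robust standard errors by linked set. In simulation (20,000 replicates, all controls linked and concordant, rho from 0.05 to 0.5) the cluster-robust tests held their false-positive rate between 4.9% and 5.5%.
- In Hypotheses 1c and 2c, keep all members of a linked set in the same cross-validation fold, so that shared information does not reach the test fold.
- State that d = 0.634/0.758 and d = 0.314 assume unlinked participants.

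The cost is one extra field and a few sentences in section F, with no added participants or procedures. The field ties a control to someone known to have HIV, so it should be coded and held under the confidentiality rules of section G. The additive cannabis interval may widen if pairs share cannabis status. If few participants are linked, results barely change.

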Serious adverse events may be reported to the IRB within the timeline outlined in their policies and procedures. The stopping criteria and guidelines to be used for this protocol may include the following: 1) The study may be stopped if there is clear evidence of harm or harmful side effects of the procedures used in this protocol; 2) In the event that a serious adverse event (SAE) occurs that increases the risks to participants, the study may be stopped and an investigation be conducted and a findings report generated by the PI; 3) Should there be an SAE or adverse event (AE) that occurs at a frequency greater than 5%, it will be added to the consent document, if not already addressed, and enrollment may be halted while a determination is made regarding the potential risks to participants. The risks of the study are low, however, the PI and study physicians as well as the WUSTL IRB will review safety material and the protocol at least annually.

F Statistical Plan

Considerations for data science methods: Continuous variables will be transformed as needed prior to analyses to improve normality and linearity of the relationship to the designated outcome variable. Raw NP tests that measure time on a task will use an inverse transformation $f(t) = 1/t$, measuring the speed of task completion; for other tests an empirical normal quantile transformation and normative corrections for demographics will be considered, which will lead to scale scores and z-scores. NP global and sub-domain values are likely to be normally distributed, which will allow for multivariable linear regression. The distributions of depression, apathy, and HRQoL scores are likely to be right-skewed and over-dispersed; therefore, negative binomial regression may be considered for analyses. All statistical tests will be two-sided, with significance declared at the $p < 0.05$ level (unless otherwise stated). In addition to hypothesis testing, 95% confidence intervals (95%CI) will be determined for effect sizes of interest. Sex will be investigated as a potential predictor of interest for each hypothesis and analysis. In exploratory analyses, correction for multiple comparisons will preserve the false discovery rate (FDR) at the 0.05 level.

Demographics: Demographic, medical, psychosocial, and lab characteristics of participants will be summarized using N (%) for categorical variables, and mean, standard deviation, and range for numeric variables.

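### The cannabis CIs within PLWH and within HIV- controls come from one four-group ANCOVA; if residual spread differs by HIV status, one is too narrow and the other too wide (minor, cheap to fix)

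*Combined protocol and SAP*

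**What the plan says.** Section F, Aim 1, Hypothesis 1a states that the inflammatory markers will be "analyzed using linear models (analysis of covariance), including as predictors cannabis status, HIV, and their interaction". Covariates are added by backward selection. The cannabis effect in each HIV stratum is taken from the same fit: it "among PLWH and HIV- controls will be reported based on these models using a 95%CI".

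Which contrast is primary depends on the interaction. If one is present, "then the primary comparison will be between CB+ and CB- groups among PLWH", at alpha 0.05. Otherwise, "In the absence of a HIV-by-cannabis interaction, the additive effects of cannabis and HIV are of primary interest". Tests are two-sided at 0.05.

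Nothing in Section F mentions robust standard errors, group-specific variances or a check of equal variance. The opening paragraph of Section F gives normality and linearity as the reasons for transforming variables. The peripheral markers are log-transformed and scaled to SD 1 before the composite is formed, and this is not described as done by group.

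**The concern.** An ordinary ANCOVA over four groups estimates one residual variance and applies it to every contrast. A contrast inside one HIV stratum then borrows half its error variance from the other stratum. If the strata differ in spread, the more variable one gets an interval that is too short and the less variable one an interval that is too long. Readers will set these two intervals side by side.

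Unequal spread is a reasonable thing to guard against. PLWH need only "be on a cART regimen for approximately ≥ 3 months, and be virally well-controlled", with no upper limit on treatment duration, while D1 calls the controls healthy. A single rescaling of a marker over the whole sample cannot change the ratio of the group SDs. At stake are the coverage of intervals that are always reported and, on one branch of the plan, the size of the primary test.

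**Working it through.** **Inputs from the documents.** Four groups of 80 (A1, B1.10, D1); two-sided alpha 0.05; 70% lumbar puncture completion (Power Analysis for Aim 1), so 0.70 × 80 = 56 per group for the brain composite.

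**Assumed input.** r = residual SD in PLWH divided by residual SD in controls, over 0.8 to 1.5. The documents give no value.

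**The plan's own figure.** For CB+ against CB- in PLWH, the plan states 80% power at d = 0.446 (peripheral) and 0.533 (brain). The normal approximation gives (1.960 + 0.842) × sqrt(2/80) = 0.443. A PLWH-only two-sample t-test (158 df) gives 0.4457, and the pooled four-group df (316) gives 0.444. With 56 per group the t-based values are 0.534 (110 df) and 0.532 (220 df). Both stated figures are reproduced.

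**Coverage with equal cells.** The pooled variance is (s_P² + s_C²)/2. The true variance of the PLWH contrast is 2s_P²/n. The ratio of reported to correct CI width is therefore

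- PLWH: k = sqrt((r² + 1)/(2r²))
- controls: k = sqrt((r² + 1)/2)

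The rejection rate with no effect is 2 × (1 − Φ(1.96k)), and coverage is 1 minus that. At r = 1.3, PLWH: k = sqrt(2.69/3.38) = 0.892, 1.96k = 1.748, rejection 8.0%. Controls: k = sqrt(2.69/2) = 1.160, 1.96k = 2.273, rejection 2.3%.

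| r | PLWH width | PLWH rejects | PLWH coverage | Control width | Control rejects | Control coverage |
|---|---|---|---|---|---|---|
| 0.8 | 113% | 2.7% | 97.3% | 91% | 7.6% | 92.4% |
| 1.0 | 100% | 5.0% | 95.0% | 100% | 5.0% | 95.0% |
| 1.2 | 92% | 7.1% | 92.9% | 110% | 3.0% | 97.0% |
| 1.3 | 89% | 8.0% | 92.0% | 116% | 2.3% | 97.7% |
| 1.5 | 85% | 9.6% | 90.4% | 127% | 1.2% | 98.8% |

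Simulation agrees at 80 and at 56 per group. The interaction and additive tests stay at about 5% throughout.

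**The two-step rule.** The PLWH test is primary only after a significant interaction. The simulated chance that both are significant, with no cannabis effect in PLWH and 80 per group, is:

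| Effect in controls only (control SDs) | r = 1.2 | r = 1.3 | r = 1.5 |
|---|---|---|---|
| 0 | 2.5% | 2.8% | 3.3% |
| 0.45 | 3.6% | 4.0% | 4.8% |
| 0.7 | 4.0% | 4.3% | 4.9% |

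At r = 1.3 it reaches 6.4% with a control-only effect of 1.0 SD and 8.0% with 1.5 SD.

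**Unequal cells for the brain composite.** Assume 48 per PLWH group and 64 per control group, that is 60% and 80% completion, averaging the planned 70%. At r = 1.3 the pooled variance is (94 × 1.69 + 126)/220 = 1.295. The model's variance for the interaction is 1.295 × (2/48 + 2/64) = 0.0944. The true variance is 1.69 × 2/48 + 2/64 = 0.1017. So k = sqrt(0.0944/0.1017) = 0.964 and the interaction test rejects in 5.9%. At r = 1.5 the same steps give 6.4%.

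**With the fix.** A variance specific to the PLWH stratum holds the PLWH test at 4.9-5.1% for r from 0.8 to 2. HC3 with three covariates gives 4.5-4.9% for r from 1.25 to 2.

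**The case against.** Four points on the other side carry weight.

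- **The gate.** A reader might infer that the primary test runs at 7-10%. The plan does not support this. That rate belongs to the PLWH contrast tested unconditionally, whereas the plan makes it primary only after an interaction test that is itself sound with equal cells. The two-step error exceeds 5% only with a large control-only effect, well above the d = 0.52 seen in the plan's preliminary PLWH comparison and contrary to Hypothesis 1a, which expects the elevation in PLWH, CB+.
- **No evidence on spread.** A reader might also infer that PLWH must vary more. No stratum SDs are given. Eligibility is weak evidence: B1.10 describes PLWH as below 20 copies/mL where D2.1 allows below 200, and both strata share the age, psychiatric and substance-use criteria. A log transform can also equalise spread where the SD scales with the mean. Neither the ratio nor its direction is known.
- **Differential effects.** It is tempting to say the plan favours concluding that cannabis acts only in PLWH. A claim of that kind rests on the interaction test. With no effect anywhere, the pattern of a significant interaction, significant PLWH and non-significant controls occurs in 2.4-3.3% with pooled variance and 1.9-2.3% with separate variances (ratios 1.2-1.5), a shift of at most 1 percentage point.
- **Detail.** The plan does not write out a common variance; that is the ordinary meaning of the named model when nothing else is specified. Robust errors for every contrast would go beyond what is needed.

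All four stand as limits. None of them reaches the stratum CIs, which are reported regardless of the interaction result.

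**Conclusion.** A minor, conditional point that holds. If residual SDs differ by HIV status, the two stratum CIs miss their nominal 95% in opposite directions: about 92% in PLWH and 97.7% in controls at a ratio of 1.3, and about 97.3% and 92.4% at 0.8. This rests on an assumed ratio and on the ANCOVA being fitted with its usual pooled variance.

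The primary decision rule is largely protected by the interaction gate. That protection weakens modestly for the brain composite if completion of the optional lumbar puncture differs by HIV status, where the interaction test rises to about 6% under the assumed 48 against 64 per group and ratios of 1.3-1.5.

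**What to change.** Add one sentence to Hypothesis 1a: contrasts of CB+ with CB- within PLWH and within HIV- controls, and their 95% CIs, use HC3 standard errors (or a model with a separate residual variance for each HIV-by-cannabis group); for the brain composite, the interaction test does too. Name one of the two methods in advance, since choosing the error term after seeing the group SDs would be data-driven. The remedy works whichever stratum is more variable.

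The cost is one software option and a negligible loss of precision when variances are equal (rejection 4.9% against 5.0%). The stated d = 0.446 already matches a PLWH-only t-test, so the power statement need not change.
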